1.1.1.3. Pharmacokinetics

The study will assess the Pharmacokinetics (PK) of etavopivat in patients with MDS. The PK endpoint is observed plasma concentration.

1.2. Study Design

1.2.1. Synopsis of Study Design

4202-ONC-203 is a multicenter, open-label Phase 2 study in adult patients with very low, low risk, or intermediate risk MDS per the Revised International Prognostic Scoring System (IPSS-R) classification. The study will enroll approximately 45 patients.

Initially, 6 patients will be enrolled and dosed a minimum of 4-weeks with etavopivat 400 mg daily to confirm if safety, exposure, and pharmacological response (PK/PD profile) are consistent with prior experience of etavopivat dosing in healthy volunteers and patients with SCD or thalassemia.

Approximately 45 MDS patients (inclusive of the initial 6 patients enrolled for safety/PK/PD confirmation) will be enrolled and evaluated for an erythroid response based on the revised MDS IWG 2018 criteria (see protocol Appendix A). Response assessment will be based on the individual patient's transfusion history in the 16 weeks prior to enrollment:

- NTD patients (received \leq 2 RBC units for anemia within the prior 16 weeks):
Hb increase of \geq 1.5 g/dL over a continuous 8-week treatment period and no transfusion of RBC units for anemia over a continuous 8-week treatment period
 - Approximately 15 NTD patients may be enrolled in this study
- LTB patients (received 3 to 7 RBC units within the prior 16 weeks): No transfusion of RBC units for anemia over a continuous 8-week treatment period
 - Approximately 15 LTB patients may be enrolled in this study
- HTB patients (received \geq 8 RBC units in the prior 16 weeks): \geq 50% reduction in RBC units transfused over a continuous 8-week period.
 - Approximately 15 HTB patients may be enrolled in this study

A futility assessment will be triggered when 15 patients across all strata or 8 patients in a single stratum reach 24 weeks of treatment, whichever occurs first. If both criteria are met at the same time, the overall futility assessment will be performed.

The futility criterion is defined as follows:

- All strata (n=15): \leq 3 responses meeting HI-E criteria, sustained from Week 16 to Week 24.
- Single stratum (n=8): 0 (zero) responses.

If either the overall or single stratum futility criterion is met, enrollment may discontinue for futility or further enrollment restricted to specific subsets of patients based on prior transfusion history may be considered. If neither criterion is met, enrollment will continue until a total of 45 response-evaluable patients are available at Week 24.

Enrollment will not pause during assessment periods unless futility analysis suggests clinical need to pause.

Patients will be enrolled into a 48-week treatment period, followed by a 28-day off-drug period. A safety follow-up visit occurs at the End of the Study (W52D1).

Novo Nordisk will perform ongoing safety surveillance. Safety surveillance activities encompass the regular periodic safety data review from clinical trials, literature surveillance and safety information derived from other sources.

If new safety signals are identified, these will be evaluated by the etavopivat internal safety committee.

1.2.2. Study Procedures

The schedule of assessments, as outlined in the study protocol, is provided in Table 1 for the Primary and Extension Treatment Periods.

Table 1: Schedule of Events, Primary and Extension Treatment Periods

Assessments	Screen	Primary treatment period														Extension treatment period												Safety follow-up visit
		W2 D1	W4 D1	W6 D1	W8 D1	W10 D1	W12 D1	W14 D1	W16 D1	W20 D1	W22 D1	W24 D1	W26 D1	W28 D1	W30 D1	W32 D1	W34 D1	W36 D1	W38 D1	W40 D1	W42 D1	W44 D1	W46 D1	W48 D1	W52 D1			
Study Day/Week(s):	D-42 to -1	W1D1 ^b	(±3 D)	(±3 D)	(±3 D)	(±3 D)	(±3 D)	(±3 D)	(±3 D)	(±3 D)	(±3 D)	(±3 D)	(±3 D)	(±3 D)	(±3 D)	(±3 D)	(±3 D)	(±3 D)	(±3 D)	(±3 D)	(±3 D)	(±3 D)	(±3 D)	(±3 D)	(±3 D)	(±3 D)		
Informed Consent (a)	X																											
Inclusion/Exclusion	X																											
Medical History	X																											
Prior ESA/Luspatercept Therapies	X																											
Prior RBC and Platelet Transfusions	X																											
Demographics	X																											
Physical Examination	X	X																									X	
Physical Examination (symptom directed)			X	X		X		X		X		X		X		X		X		X		X				X		
Height	X																											
Weight and BMI	X	X	X	X		X		X		X		X		X		X		X		X		X			X	X		
Vital Signs (including temp) ^d	X	X	X	X		X		X		X		X		X		X		X		X		X			X	X		
ECOG PS	X	X		X		X		X		X		X		X		X		X		X		X			X	X		
ECG ^e	X	X	X	X		X				X				X				X				X			X	X		
Adverse Events ^f	X																											
Concomitant Medications	X																											
Hematology ^g	X	X	X	X	X ^h	X	X ^h	X	X ^h	X	X	X	X	X	X	X	X	X	X	X	X	X	X	X	X			
Hb Electrophoresis ^g	X	X									X			X												X		
Serum Chemistry ^g	X	X	X	X		X		X		X		X		X				X							X	X		

Abbreviations: BMI = body mass index; D = day; ECOG PS = Eastern Cooperative Oncology Group performance status; ECG = electrocardiogram; ESA = Erythropoiesis-stimulating agent; Hb = hemoglobin; ICF = informed consent form; IPSS-R = International Prognostic Scoring System-Revised; MDS = myelodysplastic syndromes; PK/PD = pharmacokinetics/pharmacodynamics; PROMIS = Patient-Reported Outcomes Measurement Information System; RBC = red blood cell; The QULMS = The Quality of Life in Myelodysplasia Scale; W = week.

Note: Study visits after W1D1 must be conducted within \pm 3 days of the scheduled visit. For the purposes of assessments and analyses in this study, 4 weeks = 1 month.

- a. Informed consent must be obtained before any study-specific procedures are performed. The date of informed consent and W1D1 of study treatment may be a maximum of 56 days apart. The screening period (up to 42 days prior to W1D1 of treatment) starts only after informed consent is obtained AND a study-specific procedure is performed.
- b. W1D1 assessments should be performed prior to study drug administration and may be performed up to 3 days prior (Day -3 to Day -1).
- c. Patients who prematurely discontinue the study during the Primary or Extension Treatment Periods should complete the End of Treatment visit (W48D1) and a Safety Follow-up visit approximately 28 days after last dose of etavopipat (see Table 2).

- d. Recommend vital signs (blood pressure [BP] and heart rate [HR]) to be measured after a patient has rested for at least 5 minutes in the supine or recumbent position. A repeated measurement of HR and BP can be taken within 5 minutes if the first reading is outside the normal range and deemed clinically significant.
- e. Electrocardiograms (ECGs) (12-lead) should be recorded in triplicate. See Protocol Section 8.3.8 for detailed instructions on performing the ECGs.
- f. Adverse events are reported as described in Protocol Section 8.7.5.
- g. Assessments of iron profile (ferritin, transferrin (TIBC) and iron level) will be performed locally and will include the tests listed in Protocol Appendix E (as applicable).
- h. Hematology assessments listed in Protocol Appendix E, may be performed as outpatient/non-study center.
- i. Urinalysis will be performed locally and will include assessment for color and appearance and dipstick analysis for the tests listed in Protocol Appendix E.
- j. Serum pregnancy test will be performed locally at Screening, and a urine pregnancy test may be performed if there is any suspicion of pregnancy during the study, for all female patients of child-bearing potential (see Protocol Section 6.8.1). If a urine pregnancy test is positive, the result must be confirmed with a serum pregnancy test.
- k. MDS baseline assessment during Screening to confirm IPSS-R category and study entry criteria requires bone marrow aspirate (BMA) samples for cytomorphology and cytogenetics and peripheral blood analysis. If a screening BMA cannot be obtained, bone marrow biopsy (BMB) may need to be performed. Local analysis will be used for study entry criteria review and treatment initiation. BMA screening samples (and where indicated, with results from local analysis) will be sent to central laboratories for confirmation of study entry criteria (see Protocol Section 8.1.6).
- l. MDS response assessment includes BMA for cytomorphology and cytogenetics, and assessment of hematologic improvement.
- m. Hematologic improvement assessment only to be performed at the W24D1 visit as no BMA samples for cytomorphology or cytogenetics at W24D1 are required (unless clinically indicated).
- n. Serum for exploratory studies will be collected during Screening, pre-dose at W1D1, W4D1, W16D1, W20D1, W24D1, W32D1, W40D1, and W48D1. Fresh BMA samples, BMA smears, and peripheral blood smears for exploratory studies will be collected at Screening, W16D1, and W48D1.
- o. PD samples will be collected pre-dose on W1D1, W2D1, W4D1, W48D1 and W52D1.
- p. PK samples will be collected as follows:
 1. W1D1 and W4D1: Pre-dose (within 1 hour prior to dose), 1 hour (± 5 minutes), 2 hours (± 15 minutes), 4 hours (± 30 minutes), and 6 hours (± 30 minutes) post-dose
 2. W2D1 and W48D1: Pre-dose (within 1 hour prior to dose), 1 hour (± 5 minutes), and 2 hours (± 15 minutes) post-dose

Note: If the scheduled time for a PK/PD sample coincides with a safety ECG, the safety ECG should be performed prior to the PK/PD sample collection.

- q. After a patient discontinues study treatment and has completed their last study treatment visit, the study site may contact the patient approximately every 3 months to collect survival data.

2. PATIENT POPULATION

2.1. Population Definitions

The following patient populations will be evaluated and used for presentation and analysis of the data:

- All Enrolled Patients: This is defined as all patients who signed the informed consent form.
- Full Analysis Set (FAS): All patients who signed the informed consent and received at least 1 dose of etavopivat.
- Safety Set: All patients who receive at least one dose of etavopivat (including partial dosing).
- Efficacy Evaluable Set (EES): All patients in the FAS who have completed the Week 24 Response visit and who have a baseline record of the primary endpoint.
- Pharmacokinetic Set: All Safety Set patients who have at least one evaluable concentration for etavopivat at a scheduled PK time point after the start of dosing. For patients with protocol violations or events with potential to affect the PK concentrations, a decision regarding inclusion in the analysis will be made on a case-by-case basis and documented as part of the DBL minutes.

The Efficacy Evaluable Set is the primary population for the analysis of efficacy parameters. The PK Set is the primary population for the analysis of PK parameters. The Safety Set is the primary population for the analysis of safety endpoints. The FAS is used for demography tables.

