7.2 Treatment Discontinuation/ Withdrawal from the Study

7.2.1 Treatment Discontinuation

Treatment discontinuation is defined as any patient who permanently stops receiving study drug. A patient should be discontinued from study treatment if, in the opinion of the Investigator or Sponsor, it is medically necessary, or if it is the wish of the patient.

Patients who prematurely discontinue study drug prior to 48 weeks of treatment will have an EOT (W48D1) visit performed at the time of discontinuation followed by the Safety Follow-up visit within 28 days.

Patients must be discontinued from treatment for any of the following reasons:

- An AE that requires permanent discontinuation of study treatment
- Withdrawal of consent by the patient
- Treatment interruption for > 28 days due to a related AE
- Lack of efficacy
- Disease progression
- Pregnancy
- Patient lost to follow-up
- Investigator decision
- Noncompliance to protocol
- Termination of the study by the Sponsor

44 of 77

AEs leading to the discontinuation of study drug will be followed for 28 days after administration of last dose of study drug or until resolution, resolution to baseline, or until the event is considered stable or chronic.

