9.6 Analysis of Efficacy

The primary analysis of Efficacy will be performed using the Efficacy Evaluable Set. Sensitivity will be performed using the PPS.

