4.2. Efficacy Evaluation

Efficacy analyses will be conducted using the EES.

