4.2.1. Analysis of Primary Endpoints

4.2.1.1. HI-E Response and MDS assessments

The proportion of patients with HI-E response ≥ 8 weeks within 24 weeks of etavopivat treatment will be analyzed across the pooled strata and within each stratum. Patients will be considered responders if they satisfy HI-E criteria during any continuous ≥ 8 -week treatment interval up to W24D1.

HI-E criteria are defined based on the patient's transfusion history stratum at D1:

NTD: A patient is considered a responder where at least one continuous interval ≥ 8 weeks occurs where all of the following criteria are met:

- Hb is increased by ≥ 1.5 g/dL relative to baseline at 2 or more consecutive visits
- Relapse date (date of first Hb measurement with < 1.5 g/dL change from baseline following the qualifying increase) occurs at least 8-weeks after the first incidence of qualifying Hb increase
- Patient is free of RBC transfusions

LTB: A patient is considered a responder if they are free of RBC transfusions over any continuous 8-week period.

HTB: A patient is considered a responder if they have a $\geq 50\%$ reduction in RBC transfusion burden relative to baseline RBC transfusion burden per 8 weeks over any continuous 8-week period.

Percent reduction in RBC transfusion burden is calculated for all rolling 56-day intervals in the 24-week primary treatment period (i.e. Days 2-57, Days 3-58,..., Days 113-168) as

$$-100 \times \frac{RBC \text{ units transfused in 56 day interval} - \text{Baseline RBC transfusion burden per 8 weeks}}{\text{Baseline RBC transfusion burden per 8 weeks}}$$

The numerator for the response rate will be the total number of responders (summed across all baseline transfusion categories). The denominator will be the number of patients in the EES.

MDS baseline assessment including the score based on Revised International Prognostic Scoring System (IPSS-R) for MDS and MDS response assessment will be presented in data listings.

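### The final HI-E rate leaves out every dosed patient who stopped before the Week 24 visit, and no other final response rate includes them; the direction and size of any bias cannot be read from the documents

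*SAP*

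**What the plan says.** SAP 2.1 limits the EES to "All patients in the FAS who have completed the Week 24 Response visit and who have a baseline record of the primary endpoint". SAP 4.2 applies this set throughout: "Efficacy analyses will be conducted using the EES". For the primary rate, SAP 4.2.1.1 adds: "The denominator will be the number of patients in the EES". The Full Analysis Set (FAS, consented and dosed patients) has no efficacy role in the SAP; on its use, SAP 2.1 says only "The FAS is used for demography tables", and later sections add other descriptive tables.

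The set comes from the protocol. Protocol 9.2 defines it in the same way, and Protocol 9.6 states: "The primary analysis of Efficacy will be performed using the Efficacy Evaluable Set". Protocol 9.6 also planned a sensitivity analysis on the Per-Protocol Set, which is drawn from the FAS without a Week 24 condition. SAP 5.2 lists that set among the items not included.

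Protocol 7.2.1 lists the reasons for which treatment must stop. They include "Lack of efficacy" and disease progression. Patients who stop before Week 48 "will have an EOT (W48D1) visit performed at the time of discontinuation", followed by a safety visit.

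The response definition itself does not depend on the Week 24 visit. SAP 4.2.1.1 says "Patients will be considered responders if they satisfy HI-E criteria during any continuous" treatment interval of at least 8 weeks up to W24D1.

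**The concern.** Membership of the EES is decided after treatment starts, by an event that can depend on outcome. A patient taken off treatment at Week 14 for lack of efficacy attends an end-of-treatment visit, never has a Week 24 Response visit, and leaves both numerator and denominator. So does a patient who met HI-E for 8 weeks and then stopped at Week 20 for an adverse event. The first kind of exclusion raises the rate and the second lowers it.

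Nothing else in the SAP fills the gap. SAP 3.9 makes no substitution for missing data unless specified, and SAP 4.2.1.1 specifies none for early stoppers. The secondary transfusion-burden summary (SAP 4.2.2.1) also leaves out patients who discontinued before the end of an interval. Only the informal futility summary in SAP 3.11 counts patients who discontinued before completing HI-E assessment as non-responders, and that rule is not carried into the final analysis.

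In a single-arm study there is no control group in which the same selection would operate, so the choice of denominator passes straight into the headline result.

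**Working it through.** **1. The plan's own figure.** Inputs (Protocol 9.3, SAP 3.1): N = 45, rates 40% against 20%, one-sided 0.025, exact binomial. The smallest cut-off c with P(X ≥ c | 45, 0.20) ≤ 0.025 is c = 15 (probability 0.02499; c = 14 gives 0.0521). Power is P(X ≥ 15 | 45, 0.40) = 85.7%. The normal approximation, Φ[(0.20 − 1.96·√(0.16/45)) / √(0.24/45)] = 87.25%, matches the stated 87.3%. The design is therefore reproduced closely enough, and 15 of 45 is the smallest winning result.

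**2. Effect on the rate.** Let p be the true HI-E rate in all dosed patients, d the share who stop before Week 24 (other than through sponsor termination), and r the share of those stoppers who had met HI-E. Of N dosed patients, Np respond, Ndr of these responders are lost, and N(1 − d) patients remain. So

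EES rate = (p − d·r) / (1 − d).

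The value p = 20% is the plan's null rate, used here as an assumed truth. Values of d and r are assumptions, since the documents give neither.

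| r | d = 10% | d = 20% | d = 30% |
|---|---|---|---|
| 0 | 0.20/0.90 = 22.2% | 0.20/0.80 = 25.0% | 0.20/0.70 = 28.6% |
| 10% | 0.19/0.90 = 21.1% | 0.18/0.80 = 22.5% | 0.17/0.70 = 24.3% |
| 20% | 20.0% | 20.0% | 20.0% |
| 30% | 0.17/0.90 = 18.9% | 0.14/0.80 = 17.5% | 0.11/0.70 = 15.7% |

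In patients: 30 dosed, 6 responders and 6 early non-responders give 6/30 = 20.0% in dosed patients and 6/24 = 25.0% in the EES.

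**3. Effect on a test, if one is run.** SAP 4.2.1.1 names no test. Protocol 9.6.1 has an exact one-sided test at 0.025, taken here as a test for a rate above 20%, as in the sample-size statement. Two cases, both with p = 20%:

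- *45 dosed, no replacement.* The number evaluable is m ~ Binomial(45, 1 − d). The cut-off is found again for each m, and the rejection probability at the EES rate is averaged over m.
- *Replacement to 45 evaluable*, which SAP 3.8 permits. The probability is P(X ≥ 15 | 45, EES rate).

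| Case | r | d = 10% | d = 20% | d = 30% |
|---|---|---|---|---|
| No replacement | 0 | 4.2% | 8.6% | 16.5% |
| No replacement | 10% | 2.8% | 4.1% | 6.2% |
| Replacement to 45 | 0 | 5.8% | 13.3% | 28.8% |
| Replacement to 45 | 10% | 3.9% | 6.4% | 10.9% |

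At r = 20% there is no inflation: 1.8 / 1.7 / 1.5% without replacement and 2.5% with it.

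**4. A date rule that gives full follow-up.** The study ended early (SAP 1.1), so some patients may have been cut off before they could respond. The Week 24 protocol window ends on Day 165, but the last rolling interval for high-transfusion-burden patients ends on Day 168 (SAP 4.2.1.1) and the Week 24 analysis interval ends on Day 169 (SAP Table 3). A patient first dosed k days before termination reaches Day k + 1 on the termination date. Day 169 falls before that date when k + 1 ≥ 170, that is, k ≥ 169.

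**The case against.** The strongest reply is that evaluable-patient analysis is the pre-specified design. The protocol names the EES as primary and enrols until 45 response-evaluable patients are available, and the SAP follows it. That stands: the EES rate should stay, and its use is no departure from the protocol.

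It is also true that neither direction nor size is established. The protocol lists lack of efficacy as a reason to stop but gives no timing, so it does not show that such stops come before Week 24. Responders who stopped early are excluded too. A reader might infer that the reported rate will be inflated, or that the trial's error rate is lost. The documents do not support either: the first needs stoppers to have responded less often than the rest, and the second also needs a test that the SAP does not name. The r = 0 rows are an extreme.

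Finally, this SAP supports an abbreviated report. Disposition by analysis set and reason for stopping will be tabulated (SAP 4.1.1), and all eCRF data will be listed. The omission will therefore be visible, and a reader could rebuild the rate by hand. This lowers the weight of the point, but counts and listings are not a response rate, and the protocol's one sensitivity set has been removed.

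**Conclusion.** The point holds as a gap in reporting. The only final HI-E rate is conditional on completing Week 24, and no final response rate covers dosed patients who stopped earlier, although stopping is tied to outcome by the protocol's own list and the endpoint does not need the Week 24 visit.

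The bias may be upward, zero or downward, and its real size is unknown. On an assumed true rate of 20% with 10 to 30% stopping early, the EES rate would be too high by about 2 to 9 percentage points if no stopper responded, and by about 1 to 4 points if one in ten did. The error rates in the working apply only if the Protocol 9.6.1 test is run. The figures for 45 patients may not apply to a study that ended early. The addition is worth making because it is cheap and lets the reader see the effect, whichever way it goes.

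**What to change.** In SAP 4.2 and 4.2.1.1, keep the EES rate and report beside it the HI-E rate in dosed (FAS) patients:

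- Responder: anyone who met HI-E in any continuous 8-week treatment interval up to W24D1, even if treatment stopped later.
- Non-responder: anyone who stopped earlier without meeting it. SAP 3.11 already treats such patients this way in the informal futility summary.
- Base this rate on FAS patients first dosed at least 169 days before the termination date, whatever their reason for stopping. The documents give no termination date, so the SAP must name one calendar date for all patients.
- Show the whole-FAS rate as well, counting patients not yet responding as non-responders. This is a lower bound, because it counts patients cut off by the sponsor as failures. Identify those patients in the table.

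Record the addition in SAP 5.2. The cost is SAP wording and one or two tables, with no new data. The added rate may be lower than the EES rate, and late entrants appear only in the whole-FAS figure.

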2.2. Protocol Deviations

Protocol deviations will be assessed and documented according to the Protocol Deviation Guidance Plan (PDGP).

Protocol deviations will be classified as major and minor no later than the final data review meeting, prior to database lock. All protocol deviations will be finalized prior to the database lock and reported for all enrolled patients.

3. GENERAL STATISTICAL METHODS

3.1. Sample Size Justification

An overall sample size of N=45 will provide 87.3% power to detect an increase in the response rate for the HI-E criteria. Specifically, the assumed response rates are 40% for the etavopivat intervention and 20% otherwise (null-hypothesis comparator). One-sided testing, a significance level of 0.025, and the exact binomial distribution are used for the calculations.

